A systematic review of 2008 that evaluated the effectiveness of different interventions to promote early will in the elderly showed that most studies conducted a single educational session and measured outcomes over the next 6 months. The mean OR calculated for the performance of the document in the intervention groups was 2.6 (15). In another similar systematic review but whose population was non-terminal patients, it was observed that the majority of studies were of low quality and in the most rigorous the OR was 2.42 for different educational interventions (written materials, videos or audios).

Different ways of increasing the realization of DVA have been studied: written material only, written material with a single educational session or written material, and educational sessions. In a review of the the literature of 2007 concluded that only the multifaceted modalities increased the interest of the patients to talk about the subject with their doctors.

Tamayo et al. also observed in another systematic review that the best intervention to increase the proportions of DVA is the combination of informational material and repeated conversations in clinical visits (18).

Studies carried out in Primary Care

It is striking the good acceptance by the population towards the DVA and the scarce record of it. Angora et al., In a study in which patients aged over 65 years were interviewed in a primary care center, found that the patients were in agreement with the possibility of performing the document despite the underutilization of this resource (19). Santos et al., Also through primary care surveys, found that 97% considered it interesting, 39% said they would, and 86% did not feel uncomfortable talking to their family doctor (20). Similar results were obtained by Llordés et al. in corroborating that there was little information and much interest in this process (21).

The citizens' assessment of the possibility of making a document of advance directives is very positive, but only 1.9% in Catalonia and 0.5% in Andalusia of the respondents had done it (22,23). In Andalusia, it was also seen the importance of the information leaflet in the health center to increase satisfaction. (23)

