Regarding intervention studies to increase the records of DVA performed in Primary Care, we have that of Donahue et al. who obtained a 32.5% increase in VAD by mailing the information prior to the arranged visit with their family doctor and completing it in successive visits in a period of 3 months (24).

Wisow et al., In a quasi-experimental study of 1 year duration, promoted the anticipated will in over 65 in health centers through oral and written education (a letter prior to a control visit and a subsequent reminder visit) administered by

family doctors and used another health center as a control. The result was an increase of 7'8% of registrations with respect to <1% in the control center (25). According to another study in Primary Care (Ramsaroop, 2007), the information leaflet alone is not effective and the best would be multiple educational visits to promote the attitude change phase towards the ADs procedure (26).

Hypothesis of the study

Giving brief oral and written information to patients visited by your family doctor on a prior appointment increases the proportion of DVA records by 8%.

Providing a brief oral and written information to patients visited by their family doctor in a previous appointment increases the proportion of people interested in this right (there is no previous bibliography on this data).

People who write a DVT are usually older, white, women, have more children, have a will and have more comorbidity than those who do not.

MAIN OBJECTIVE

To evaluate the effect of brief oral and written information on the advance directive document (DVA) administered by primary care physicians, compared to usual clinical practice, on the proportion of persons interested in or performing the VAD in 3 months in the adult population (over 18 years old) who attend a Primary Care appointment.

SECONDARY OBJECTIVES

Evaluate the baseline characteristics of those who perform or are interested in VAD (whether they are in the control or intervention group).

To assess the baseline characteristics of those performing the DVA and those not within the intervention group.

Evaluate the reasons why patients finally formalize the document by open question (will be categorized if there is a limited number of responses, otherwise the reasons will be described qualitatively).

Evaluate the average time to perform the DVA from the day of the patient's recruitment.

MATERIAL AND METHODS

Design

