Parallel group unicentric randomized clinical trial. Prospective primary care intervention study.

For randomization, randomly generated numbers will be used in closed envelopes controlled by a professional outside the study. Subsequent masking is not appropriate for the patient. The randomization unit will be the patient.

Sample

Open-label (or non-blind) unicentric randomized clinical trial of parallel groups. Simple random sample of patients who go to an appointment with their family doctor.

Inclusion criteria: Patients older than 18 years old who go to their family doctor by appointment.

Exclusion criteria:

- Patients with language barrier
- Patients younger than 18 years (AD not provided for by law) (28)
- Patients with altered decision-making ability according to computerized clinical history by coding in health problems or mentioned in a clinical course of computerized medical history (eCAP): cognitive impairment, dementia, mental retardation diagnosed. Although there are studies on attitudes towards ADs of people with early cognitive impairment (Minimental > 18), it was decided to discard because the intervention should be brief. The cited study also concludes that this type of patients prefer to delegate decisions to the family. (29)
- Patients who come spontaneously to their family doctor.
- Patients who have already been recruited previously in the study. Patients who may visit by appointment only on more than one occasion will only participate once and subsequent visits for recruitment will be excluded. In addition, there will be no reinforcement of the study intervention in these visits.
- Patients who have already formalized the ADs.
- Patients who do not wish to participate in the study.

Calculation of sample size: In order to know the magnitude of the effect of similar studies in primary care with similar interventions (written and oral information vs no intervention), the Wissow study (25) was chosen, where the proportion of VAD obtained in intervention group was 7.8% vs. <1% in the placebo group.

In calculating proportions in cohort studies or clinical trials:

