Accepting an alpha risk of 0.05 and a beta risk of 0.2 in a bilateral contrast, 165 individuals in the intervention group and 165 in the control group are required to detect a minimum relative risk of 7.8 (= 7.8% / 1%) taking the rate of VAD in the intervention group as 7.8% and in the control group of 1%. A rate of loss has been estimated for refusing the 10% share. The POISSON approximation has been used in the statistical calculator GRANMO, version 7.12 online (Program of Research in Inflammatory and Cardiovascular Disorders, Institut Municipal de Investigació Mèdica, Barcelona, Spain)

Although hypothetically no losses are expected, they may have been relinquished to participate for different reasons. In order to avoid a selection bias produced by the relationship of giving up with the fact of wanting to do a VAD, patients refusing to participate will be excluded and the motive, age and sex will be collected to compare if there are differences between the two groups regarding these characteristics.

Ambit

Florida Nord de l'Hospitalet de Llobregat Primary Care Center, an urban area with a population of approximately 25,000 people. Multicultural neighborhood with low socioeconomic status. The follow-up time for the intervention will be 3 months.

Information sources

Records of shared clinical history in eCAP. Patient questions about independent variables if they are not recorded.

Recruitment procedure

Consecutive recruitment: They will be consecutively obtained from different quotas (both afternoon shift and morning shift) so that the sample is representative of the study population.

Participate the quotas of the center whose doctor in charge has wanted to participate in the study. In order to avoid a selection bias and a more active doctor than another to have more patients represented in the study, a mechanism will be established whereby everyone will have the same probability of recruiting a similar number: the first 6 visits of each day for 8 days. The recruitment period will be made from 01/06/2015 to 09/30/2015, until the sample is completed. The follow-up period will be 3 months for each patient (both intervention and control).

A list of random numbers will be created and divided among the 7 consultations of the participating physicians in the study. Each day, the first 6 visits to the list will be recruited for 8 days prior appointment or until the sample is completed.

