Patients will be randomized according to the list of random numbers guarded by a professional (or several) other than the study that will be located in the adjacent consultation. In case there is no professional close, the list will be delivered with a

closed envelope to another professional and will be contacted by telephone. Patients will be treated with the intervention when the number is 1 and control if it is 0. This number will be asked prior to the patient's entry into the consultation.

Predictive or independent variables to be obtained at the time of the first visit

For stratified analysis.

- Sex: Male, Female
- Race: Caucasian vs non-Caucasian
- Age in years
- Level studies: Primary, secondary, university, without studies.
- Comorbidity: measured by the Charlson index. Score: a) 0-1: no comorbidity; b) 2: low comorbidity; c) ≥ 3 : high comorbidity.
(Charlson.webloc calculator).
- Testament on material goods: Yes, no.
- Religious Confession: yes, no. Is considered a practitioner: yes, no
- Marital status: single, married, widowed, separated / divorced
- Number of children

To obtain this information will be extracted from the computerized medical history or the patient will be asked.

Intervention

Patients who are included in the intervention group, if they meet the inclusion criteria and do not present any exclusion criteria, will be given brief information about the existence of the document of anticipated wills after resolving the reason for the visit for which they had come the patient. This information will not last more than 3 minutes and will not be repeated on successive visits within the recruitment period. Also, an informative triptych (see attachments) will be given to the patient so that he can read it at home. These leaflets have been made by the Department of Health of the Generalitat de Catalunya. They will be advised that we can extend the information if they are interested or help them to do the document in the near future if they want, we will inform you that we would wait for the answer before 3 months (24). In case of interest, you can leave your information in the User Service of the outpatient clinic by specifying name, telephone number and reference doctor or ask for an appointment again.

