Patients who fall into a control group will only be attended to their reason for visiting and will be asked for the necessary data to obtain the independent variables if they do not appear in their history. If the patient in this group wants the information, he will be excluded from the study because he "refuses to participate."

If the patient, both the control group and the intervention group, has some exclusion criteria, it will be recorded as a screening failure and their randomization number will not be re-used for the next patient.

All patient information will be kept confidential.

Result or dependent variables

They will be obtained at the moment that the patient shows interest in the intervention, or else, by asking by appointment or by telephone within 3 months of their recruitment:

- Interest in information about DVA: yes, no. Number of patients who have come to their family doctor (MF) to request information or have been interested by telephone in each group.

- Implementation of DVA: yes, no. Number of patients in each group.

In case of not being able to contact the telephone patient or face to face at 3 months, the DVA registration will be viewed at the Primary Care Clinic Station (eCAP), which is the computerized medical history program used by all professionals in the network of primary care of the Institut Català de la Salut (ICS).

The document can be accessed from:

- HC3 - Notices: shared clinical history projects in Catalonia.

- Dades del pacient: Documents of anticipated voluntats

Registration from the Department of Health is autonomous, although not done in the ABS. From other institutions, the patient is always advised to take the DVA to his health center.

- Open question to know the reason that has led to formalize the DVA, both to patients in the intervention group and control.

- Time to perform the DVA from the day of recruitment, expressed in days, to both the intervention and control patients.

Limitations and ethical considerations

- Possible increase in response in the intervention group due to the link with the family physician (participation bias). It could be wrongly concluded that the intervention is effective when compared to the control group. Randomization of the sample is intended to partially avoid this problem.

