- Possible contamination of the groups when living in the same neighborhood and the possibility of communication between the patients in the control group and the intervention group. To find out this, patients in the control group will be asked to become interested or to do DVA if they have been informed by other patients of the study through the questions: Do you know anyone else who participates in this study? Did you talk about the study with that person?

- Bias of hyper-attendees: they are more likely to be chosen for the study however this problem is within usual clinical practice. The information will not be repeated to the patient who has already been randomized.

The study has been submitted to the Ethical Committee for Clinical Research (CEIC) of the University Institute for Research in Primary Care (IDIAP) Jordi Gol, and is awaiting the results of its evaluation. When accessing the eCAP and / or performing a personal interview to complete information on the variables is required, the patient's signed informed consent will be requested through his physician. The confidentiality of the subjects included in the study will be

guaranteed according to the Organic Law on Protection of Personal Data (15/1999 of December 13, LOPD). Researchers are committed to maintaining the confidentiality of information, working with anonymous patient data, and respecting current ethical and research practice standards.

Statistical Analysis Plan (SAP)

Intention-to-treat analysis. No intermediate analysis is planned. A bilateral significance level of 5%, 95% CI and 80% power will be used. The SPSS V21 program will be used. Analysis of efficacy of unadjusted parallel clinical trials. Data will be analyzed according to the CONSORT guidance and comparisons between groups will be based on the intention-to-treat principle. First: analysis of the baseline comparability of the study groups in relation to the variables studied. Descriptive statistics of all variables collected. The Student's t test or the Mann-Whitney U test (according to the frequency distribution of the variables studied) will be used to compare continuous variables, and Chi-square or Fisher's exact test for comparison of categorical variables.

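### The outcome contact is timed both within and at 3 months; the first timing lets staff raise advance directives with either arm before the outcome window closes

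*Protocol*

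**What the plan says.** The Protocol's section on result or dependent variables gives two timings for the same contact. Outcomes are taken when the patient shows interest or otherwise "by asking by appointment or by telephone within 3 months of their recruitment", with no earliest date. The fallback to the electronic record (eCAP, with the shared clinical history HC3) is then introduced with "In case of not being able to contact the telephone patient or face to face at 3 months". That lookup is described only for patients who could not be contacted. The SAP does not say when outcomes are ascertained.

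The outcome window is the same 3 months. The main objective is the effect "on the proportion of persons interested in or performing the VAD in 3 months", and the recruitment section gives each patient in both arms 3 months of follow-up. Interest counts if the patient comes to the family doctor to ask for information or expresses it by telephone.

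Three places limit the intervention to a single contact:

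- Exclusion criteria, on later appointments: "In addition, there will be no reinforcement of the study intervention in these visits".
- Intervention section: the oral information "will not be repeated on successive visits within the recruitment period".
- Limitations section: "The information will not be repeated to the patient who has already been randomized".

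Controls are to be seen only for the reason they came, apart from baseline data. The contamination paragraph considers only conversation between patients.

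**The concern.** A question about ADs put by the study before month 3 is more than measurement. For a control it is the practice raising the subject. For an intervention patient it is a second mention. Either patient can still act on it inside the window. The Protocol's own literature review reports that the best way to raise AD rates is "the combination of informational material and repeated conversations in clinical visits". That finding is not about a single outcome question, but it makes a second mention plausibly active.

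The comparison intended is one brief contact against usual practice. Prompted controls shrink that contrast. Reminded intervention patients turn the treatment into information plus a reminder. The interest component is the more exposed, because interest expressed by telephone counts and the call itself may elicit it.

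There is also an opposite fault. No passage says that a patient who answers no early is asked or looked up again at 3 months. If not, that patient's follow-up ends at the early contact and a later AD is lost.

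**Working it through.** **1. What the text allows for a patient asked before month 3**

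| Handling after an early no | Consequence |
|---|---|
| Rechecked at 3 months | An AD prompted by the question is counted |
| Not rechecked | Follow-up is cut short and a later AD is missed |
| Contact made only at 3 months (the section's second timing) | Neither problem for AD completion; the call can still elicit interest |

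The documents do not choose between these rows.

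**2. The plan's own figure.** Inputs from the sample-size paragraph: 7.8% versus 1%, two-sided alpha 0.05, power 0.80, Poisson approximation, 10% loss.

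n = (1.960 + 0.842)² × (0.078 + 0.01) / (0.078 − 0.01)² = 7.849 × 0.088 / 0.004624 = 149.4 per arm.

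Allowing for loss, 150 × 1.10 = 165 (149.37 / 0.90 = 166.0). The stated 165 per arm reproduces, and this point does not dispute it.

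**3. Power if the question prompts ADs.** I use 149 evaluable per arm (165 × 0.9 = 148.5). Expected control ADs are 149 × 0.01 = 1.5, and at a 2% rate 149 × 0.02 = 3.0. A shift of one point is therefore about 1.5 extra ADs.

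Exact power is the sum, over all pairs (a, b) for which the test rejects, of Bin(a; 149, p₁) × Bin(b; 149, p₀). The test is Pearson chi-square, or Fisher's exact test when any expected count is below 5, two-sided 5%. The plan names both tests but gives no rule for choosing, so the expected-count rule is my assumption. All rates below the first row are also assumptions, because the documents give no size for a prompting effect.

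| Intervention | Control | Difference (points) | Relative risk | Exact power |
|---|---|---|---|---|
| 7.8% | 1% (as planned) | 6.8 | 7.8 | 0.850 |
| 7.8% | 2% | 5.8 | 3.9 | 0.659 |
| 7.8% | 2.5% | 5.3 | 3.1 | 0.552 |
| 7.8% | 3% | 4.8 | 2.6 | 0.449 |
| 8.8% | 2% | 6.8 | 4.4 | 0.77 |
| 9.8% | 2% | 7.8 | 4.9 | 0.85 |
| 8.8% | 1% | 7.8 | 8.8 | 0.92 |

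Rows two to four prompt controls only. Rows five and six prompt both arms. The last row reminds the intervention arm only, and there the effect of a single contact is overstated.

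**4. Interest.** The documents give no expected rate for interest, and the hypothesis section says there is no earlier literature on it. No power figure can be given for that component.

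**The case against.** The strongest reply is that the section, read as a whole, means one contact at the end of follow-up. It does speak of contact at 3 months, follow-up is 3 months for everyone, and the English is plainly a translation, so the word within may carry little weight. No passage plans opportunistic asking at early visits. This stands as far as it goes: the text is ambiguous and is not a clear plan to ask early. But seven physicians will follow it, and one of its two timings sets no earliest date.

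A reader might infer that the plan breaks its own no-reinforcement rule. The documents do not support that. The three statements bar reinforcing the intervention or repeating its information, and asking whether someone has made an AD is neither. The question works against their purpose, not their letter.

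A reader might also infer that prompted ADs are bound to be counted. That is not stated either, since the record lookup is described only for patients who could not be contacted.

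Nor is the question shown to be a control's first notice of ADs. Signed consent is requested, and the plan foresees controls who want the information. What the consent sheets disclose cannot be seen here. Earlier awareness would make a later prompt less novel, but not necessarily inert.

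Finally, a fall in power to 45% requires the control rate to triple while intervention patients do not respond at all. If both arms respond, the loss is smaller or absent.

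**Conclusion.** The concern holds as an unresolved ambiguity with a real consequence. The Protocol allows the outcome question before the window closes, sets no date for it, does not say what follows an early no, and does not list prompting by the question as a limitation. The estimate could then be diluted, inflated or based on shortened follow-up, and the documents do not determine which or by how much.

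The illustration shows only that the design is sensitive. With about 1.5 control ADs expected, about 1.5 more in that arm alone takes exact power from 85% to 66%. One point in both arms gives 77%, and two points in the intervention arm with one in controls leaves it at 85%. These figures rest on assumed prompting rates, 149 evaluable per arm, and AD completion only. It would be too strong to say that the trial will lose power, or that the plan contradicts its no-repeat rule. The correction is worth making because it is cheap and removes every one of these possibilities.

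**What to change.** In the section on result or dependent variables, and in the SAP:

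1. Replace the within-3-months wording with one contact time for both arms, at or after the end of each patient's 3-month window. State that the study puts no question about ADs to any patient between the recruitment visit and that contact.
2. Before the contact, take AD completion from eCAP/HC3 by AD date for all patients, not only those who cannot be reached.
3. Count only ADs dated within 3 months of recruitment. Include those reported at the contact but not yet in the register, since the Protocol notes that documents made through other institutions depend on the patient bringing them in.
4. Log interest that the patient raises unprompted during the window, when it occurs. Do not count interest first voiced in reply to the outcome question.

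The cost is a change of wording, somewhat more calls after month 3 because earlier routine visits can no longer be used to ask, and perhaps a few more patients not reached. Record access is already planned, and the sample size stays at 165 per arm.

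### Prior advance directives are excluded with no stated check before allocation, and the completion outcome carries no date rule, so an old directive could count as an event, most likely in the control arm

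*Protocol*

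**What the plan says.** **Eligibility.** The exclusion list in the protocol's Sample section includes "Patients who have already formalized the ADs". The cognitive exclusion in the same list names its source (coding or notes in the computerised history). The AD exclusion names neither a source nor a time.

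**Order of events.** Under Recruitment procedure, the random number is requested before the patient comes in. Under Intervention, a patient in either arm who proves to meet an exclusion criterion is logged as a screening failure and the number is not used again.

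**Content of the visits.** The intervention visit includes a short talk on ADs, a leaflet and an offer of help. For the other arm, "Patients who fall into a control group will only be attended to their reason for visiting", apart from questions needed to fill in the independent variables. Those variables include a will on material goods but not an existing AD.

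**Outcome.** Under Result or dependent variables, completion is "Implementation of DVA: yes, no. Number of patients in each group". It is obtained by asking the patient or, if contact fails, by looking for a registration in eCAP. Neither route has a date condition. Days from recruitment to AD are collected in both arms, but the SAP uses them only for a descriptive secondary objective. The main objective, in the protocol and the SAP, does limit completion to three months.

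**Record coverage.** The same section names eCAP and the shared Catalan history (HC3) as places where an AD can be seen, and describes Department of Health registration as autonomous. It adds: "From other institutions, the patient is always advised to take the DVA to his health center".

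**The concern.** Two gaps act together.

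First, eligibility on prior AD can be settled after the arm is known, and the topic that would bring a prior AD to light is raised by design in one arm only. A holder whose AD is not in the record may mention it during the talk and be dropped. A similar patient in control has no set occasion to mention it and stays in. Exclusion after a known allocation, at rates that may differ by arm, sits badly with the intention-to-treat principle in the SAP.

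Second, the variable that feeds the analysis does not carry the objective's window. If a retained holder reports an AD at follow-up, or the eCAP look-up finds one, no written rule stops it being scored as yes.

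The plan expects fewer than two completion events among controls, so one or two old ADs there would matter. The bias would be towards no effect.

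**Working it through.** **Inputs from the protocol.** Two-sided 5% test, 80% power; completion 7.8% v 1%; "165 individuals in the intervention group and 165 in the control group are required", with a 10% loss allowance (Calculation of sample size). AD prevalence in surveys: "only 1.9% in Catalonia and 0.5% in Andalusia of the respondents had done it" (Studies carried out in Primary Care).

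**Assumptions, not in the documents.** That 1.9% applies at this centre, and the share *f* of prior holders missed at entry, taken as 10%, 25% and 50%.

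**Step 1: the plan's own figure.** With the Poisson variance, n = (1.960 + 0.842)² × (0.078 + 0.01) / (0.078 − 0.01)² = 7.849 × 0.088 / 0.004624 = 149.4, so 150. Then 150 × 1.1 = 165 (150 / 0.9 would give 167). The stated 165 reproduces.

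**Step 2: scale.** Planned control events: 165 × 0.01 = 1.65. Prior holders among 165 patients at 1.9%: 165 × 0.019 = 3.1, before any screening.

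**Step 3: detection in the intervention arm only.** Let q = 0.019 × f. The control rate becomes 0.01 + q; the intervention rate stays at 0.078. Exact two-sided Fisher power sums the binomial probabilities of all tables with p ≤ 0.05, at 165 per arm. As a check, the pooled normal approximation is Φ{[d − 1.96√(2p̄(1−p̄)/n)] / √[(p₁(1−p₁) + p₂(1−p₂))/n]}.

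| Missed at entry | Old ADs in control | Control rate | Risk ratio | Fisher power | Normal approx. |
|---|---|---|---|---|---|
| none | 0 | 1.00% | 7.8 | 84% | 86% |
| 10% | 0.3 | 1.19% | 6.6 | 80% | 83% |
| 25% | 0.8 | 1.48% | 5.3 | 74% | 78% |
| 50% | 1.6 | 1.95% | 4.0 | 62% | 70% |

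For the last row, d = 0.0585 and p̄ = 0.04875, so (0.0585 − 1.96 × 0.02371) / 0.02349 = 0.51 and Φ = 0.70. The Fisher column is sensitive to exact arm sizes (5 v 0 events gives p = 0.061 at 165 v 165 but 0.030 at 164 v 165). Read it for the size of the drop more than for the level.

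**Step 4: both arms miss old ADs equally.** Adding q to both rates leaves the difference at 6.8 points. Fisher power is 82%, 79% and 74% at 10%, 25% and 50% missed. The loss is smaller but not zero, so the missing date rule matters even without any difference between arms.

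**Step 5: lower prevalence, intervention-arm detection as in step 3.** At 1% prevalence, Fisher power is 82%, 79% and 73%. At 0.5% (the Andalusian figure) it is 83%, 81% and 79%.

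**Step 6: what the calculation leaves out.** The main objective is interest in or completion of an AD. The plan gives no rate for interest, so these figures cover completion only.

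**The case against.** The strongest reply is that this is a drafting gap with a small practical effect. Its parts deserve separate answers.

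- *The window is already in the objective.* True, and an AD dated before recruitment has no sensible value for days from recruitment. A careful analyst might catch it. But no rule links that variable to the yes/no outcome, and the eCAP fallback looks only for a registration. A reader might infer that the plan accepts old ADs as events. The documents do not support that: the objective points the other way, and the fault is that the variable definition does not carry it through.
- *Differential detection is nowhere stated.* Correct. The exclusion applies to both arms, and the record could be checked in both. The provisions for a control patient who wants the information, and for asking controls about others in the study, suggest that controls may know the topic. The information sheets were not available for this review. The mechanism is plausible, not documented.
- *The record may miss few ADs.* A reader might take the sentence about other institutions to mean that such ADs reach the centre only if the patient brings them. The text does not say only, and it also names HC3 and autonomous registration. A small missed share is credible, and at 10% missed Fisher power is still 80%.
- *The 1.9% may be too high here.* The protocol describes a neighbourhood of low socioeconomic status and cites lower completion in low social classes. That stands; step 5 shows the effect.

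What survives is the order of allocation and eligibility, the removal of patients after allocation, and the absence of a date rule.

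**Conclusion.** The point holds as a correctable weakness in the eligibility sequence and the outcome definition. It does not show that the trial will be biased by a known amount. The sequence and the missing date condition are in the text. More frequent removal of prior holders from the intervention arm is an inference from the content of the two visits.

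The direction, if it occurs, is towards no effect on completion. The size runs from negligible (10% missed, or low prevalence) to a loss of about 22 points of Fisher power (84% to 62%) at 1.9% prevalence, half of prior holders missed and detection in the intervention arm only. With equal detection the corresponding loss is about 10 points (84% to 74%). None of this changes the sample size, and nothing is claimed about the interest outcome. The change is worth making because it is cheap and so few control events are expected.

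**What to change.** 1. Check the eCAP/HC3 AD record of each listed patient before the random number is requested, and exclude prior holders at that point. The protocol ties eCAP access to signed consent, so the timing must fit whatever arrangement the ethics section requires.
2. State in the outcome definition that completion counts only if the AD is dated from recruitment to three months. Apply this to patient reports and to the eCAP fallback, with the date recorded for every AD.
3. If a prior AD comes to light after allocation in either arm, keep the patient in the intention-to-treat denominator as having no new AD, and report the number by arm.

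The cost is a small amount of record checking, one date field and a sentence or two of text. Item 3 leaves in the denominators a few patients who cannot have the outcome. Even at q = 0.95% in both arms (1.9% prevalence, half missed), this shrinks the expected difference only from 6.8 to 6.8 × (1 − 0.0095) = 6.7 points. The record check will not find unregistered ADs, which is why items 2 and 3 are needed as well.
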